4.1 OVERVIEW OF STUDY DESIGN/INTERVENTION

4.2 Design

Patients enrolled in this study will undergo LDR prostate brachytherapy followed approximately 4 weeks later with hypofractionated, image-guided intensity modulated radiation therapy to a dose of 25Gy in 5 fractions of 5Gy delivered every other day. Radiobiologically, as indicated in the BED calculations in Section 3, the dose of hypofractionated radiotherapy is expected to have less acute toxicity and equivalent late toxicity as standard fractionated treatment. Both brachytherapy and hypofractionated external beam radiation therapy will be delivered using the same equipment, techniques and treatment planning procedures as currently practiced at MSKCC.

Patients will be followed post-treatment at 1, 3, 6 (+/- 4 weeks) and every 6 months (+/- 4 weeks) thereafter until 36 months. During the post-treatment followup, patients will be evaluated for urinary, bowel/rectal, and sexual toxicity. Baseline measures of these domains will be obtained prior to treatment. The primary endpoint will be urinary toxicity as assessed by CTCAE v4.0 at 12 months. Bowel and sexual function will also be assessed at followup as

secondary endpoints. Serum PSA levels will be drawn on the same schedule as clinical followup. Post-treatment prostate biopsies will be obtained once at 24-36 months post-treatment to evaluate pathologic response to therapy.

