9.1 TREATMENT/INTERVENTION PLAN

Brachytherapy Procedure (all steps as per current departmental procedure):

- Patients undergo general anesthesia for outpatient interstitial brachytherapy
- Transrectal guidance of implanted fiducial markers into the prostate
- Transrectal ultrasound utilized to guide needles/seeds into the prostate gland
 - LDR procedure:
 - Pd103 radioactive seeds inserted according to intraoperative plan using MICK applicator and ultrasound/fluoroscopic guidance.
 - Prescription dose= 100Gy to the prostate
 - Postoperative CT-based dosimetry following procedure
- Following completion of brachytherapy treatment, Foley catheter removal and voiding trial
- Discharge home

Hypofractionated Radiation Therapy:

Simulation (all steps as per current departmental procedure):

- Approximately 2 weeks following interstitial brachytherapy, a simulation for hypofractionated external beam radiation therapy will take place.
- A bowel preparation will be performed the night before simulation.
- Patients will be instructed to maintain a full bladder during simulation and treatment.
- Patients will be supine and positioned in a thermoplastic mold.
- A Foley and rectal catheter will be placed for simulation only.
- CT images will be obtained as per existing department protocols and used for treatment planning purposes.

Treatment Planning:

- The gross tumor volume (GTV) will be defined as the prostate gland.
- The clinical tumor volume (CTV) will be defined as the prostate and seminal vesicles.

- The planning target volume (PTV) will be defined as a non-uniform expansion around the CTV: 0.5cm in all directions except posteriorly at the rectal interface which will be 0.3cm.
- Normal tissues to be contoured include:
 - Bladder wall (inner and outer)
 - Rectal wall (inner and outer)
 - Urethra
 - Bilateral femoral heads/neck
 - Large bowel
 - Small bowel
- The following dose constraints will be used for treatment planning:

PTV D95% [Dose to 95% volume]		90%
Rectal wall max	106% of Rx	2650 cGy
Rectal wall D1cc [Dose to 1cc]	103% of Rx	2575 cGy
Rectal wall mean dose		1550 cGy
Urethra max	100% of Rx	2500 cGy
Urethra D1cc [Dose to 1cc]	90% of Rx	2250 cGy
Bladder wall max	106% of Rx	2650 cGy
Bladder wall D5cc [Dose to 5cc]	103% of Rx	2575 cGy
Bladder wall mean dose		1650 cGy
Small/Large Bowel max		2500/2650 cGy
Femur max		2000 cGy

Treatment delivery:

- Patients will be treated every other day (as per standard hypofractionated treatment) Monday- Friday

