10.1 EVALUATION DURING TREATMENT/INTERVENTION

Patients who cannot meet the necessary dosimetric constraints will not be eligible for participation in the study and will be withdrawn from study, since they will already be enrolled at this time

- There will be at least one status check visit during the course of hypofractionated external beam radiotherapy.
- Participants will have clinic follow-up visits at 1, 3, and 6 months (+/- 4wks) posttreatment.
- Then at 6 month intervals (+/- 4wks) post treatment.
- Follow-up scheduling is based on the last day of hypofractionated treatment.
- At each followup visit, patients will undergo standard DRE and serum PSA. Patients will also be asked to complete sexual quality of life questionnaires (EPIC), and urinary and rectal quality of life questionnaires (IPSS and IIEF), which will be captured per standard of care and be assessed for toxicity using CTCAE 4.0. If patient is unable to come in for a followup appointment, a telephone followup will suffice and the PSA and DRE will be deferred. IPSS, IIEF, and EPIC questionnaires can be completed over the phone or sent to patients via mail, fax, or electronic mail by the physician or the physician's office assistant if the patient is unable to come in for a follow-up appointment. If the patient cannot be reached by phone or prefer to complete the questionnaires personally, the questionnaires will be sent via mail, fax or electronic mail. The questionnaires sent directly to patients must be blank forms with no patient identifiers, only study ID numbers. If questionnaires are sent via mail, the patient must be provided with a pre-filled business envelop that will allow patients to return it with no expense. Patients must also have the option of returning questionnaires by electronic mail or fax. If a patient is unable to come in for a follow-up appointment or complete the questionnaires over the phone, the method by which questionnaires are sent to patients and the method by which questionnaires are returned will be determined based on the patient's preference or if they are unable to be contacted by phone, the contact information on file for the patient as some patients may not have access to a phone, fax or electronic mail. A repeat prostate biopsy will be completed between months 24 and 36 for pathologic response assessment. This is a standard assessment tool.

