After 36 months, patients will be encouraged and have the option of continued followup through our Prostate Survivorship Clinic for as long as feasible. Continued quality of life (IPSS, IIEF) and disease (PSA, DRE) assessment will be as per standard practice in the Prostate Survivorship Clinic.

	Prior to brachy therapy start unless otherwise indicated	During RT	Month 1, 3, and 6 (+/- 4 weeks)	Month 12-36 (every 6 months +/- 4 weeks)	Once during year 2-3
Pathology review	X				
History and PE	x ¹				
DRE	x ¹		X	X	
PSA	x ¹		X	X	
Prostate biopsy	X (if				X

	applicable)				
Pelvic MRI or CT	X ²				
Bone scan (if deemed necessary)	X ²				
Toxicity assessment (CTCAE 4.0, IPSS, IIEF, EPIC)	X ^{1, 3, 4}		X ⁴	X ⁴	X ⁴
LDR Brachytherapy		X (Once)			
IG-IMRT (every other day)		X			
Status check		X (Once)			
Followup			X	X	X

1 Within 6 weeks of enrollment; comorbidities are captured at baseline

2 Within 6 months of enrollment

3 IPSS, IIEF, and EPIC repeated within 4 weeks prior to brachytherapy for patients undergoing cytoreductive hormone therapy

4 Standard of care IIEF and IPSS Questionnaires will be used

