12.1 CRITERIA FOR THERAPEUTIC RESPONSE/OUTCOME ASSESSMENT

The primary objective of this study is to assess toxicity associated with combined LDR brachytherapy and hypofractionated radiation therapy for intermediate risk prostate cancer at 12 months via CTCAE v4.0. Both acute and late toxicity associated with radiation therapy will be evaluated in a fashion similar to those used in prior studies of radiation therapy in prostate cancer patients. All grade 2 or higher toxicities will be evaluated and attributed to radiation therapy or not. Evaluation will be carried out prior to treatment to serve as a baseline. During each subsequent followup visit, patients will be asked to complete questionnaires (IPSS, IIEF, and EPIC) and asked about symptoms. The primary expected toxicities are genitourinary and gastrointestinal (rectal). Sexual function assessment is included but is not considered an SAE.

The following instruments will be used in the evaluation of toxicities:

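### No CTCAE or IPSS assessment is scheduled from the implant to the month-1 visit after external beam (nominally 67–69 days), so transient grade 1–2 acute toxicity is not systematically graded

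*Combined protocol and SAP*

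**What the plan says.** In the Section 10.1 schedule table, the row labelled "Toxicity assessment (CTCAE 4.0, IPSS, IIEF, EPIC" is marked at baseline, at months 1, 3 and 6, at the half-yearly visits from month 12 to month 36, and once in year 2–3. Its cell in the during-RT column is empty, although that column is marked for the implant, the external beam course and the status check. The Section 10.1 text likewise ties the questionnaires and CTCAE grading to follow-up visits, and it sets the clock: "Follow-up scheduling is based on the last day of hypofractionated treatment". The first visits are then fixed: "Participants will have clinic follow-up visits at 1, 3, and 6 months (+/- 4wks) posttreatment".

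Two contacts already fall between the implant and month 1. Section 9.1: "Approximately 2 weeks following interstitial brachytherapy, a simulation for hypofractionated external beam radiation therapy will take place". Section 10.1: "There will be at least one status check visit during the course of hypofractionated external beam radiotherapy". No toxicity instrument is named for either.

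Against this, Section 12.1 promises: "Both acute and late toxicity associated with radiation therapy will be evaluated in a fashion similar to those used in prior studies". It adds that every toxicity of grade 2 or above will be assessed and attributed, or not, to radiation. Section 14.0 will tabulate all toxicities by type and grade. Section 4.2 states an expectation: "the dose of hypofractionated radiotherapy is expected to have less acute toxicity and equivalent late toxicity as standard fractionated treatment". Section 11.1 divides early from late toxicity at 90 days from treatment, without saying which component starts the count.

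For men given hormone therapy before the implant, Section 8.1 and footnote 3 of the table repeat IPSS, IIEF and EPIC within 4 weeks before brachytherapy. CTCAE is not among the repeated instruments.

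**The concern.** The regimen has two radiation components about four weeks apart, and scheduled grading starts only about a month after the second has ended. A grade 1 or 2 urinary or rectal event that arises after the implant or during external beam, and settles before month 1, has no scheduled occasion on which to be graded. Nor is there a scheduled grade that shows a patient's state when the hypofractionated course begins, and that course is the new element of the combination.

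At stake is what the trial can report about acute toxicity. Section 3.0 describes the combination as not yet studied and gives establishing its toxicity as the purpose of the study. Acute grades that are not collected at the time are hard to recover later.

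**Working it through.** **1. Number of assessments.** Section 12.1 says EPIC, which shares the toxicity row, will be presented at nine assessment times. Baseline plus months 1, 3, 6, 12, 18, 24, 30 and 36 is 1 + 8 = 9. That accounts for all nine and leaves none between the implant and month 1. The separate year 2–3 mark falls within months 24–36 and does not bear on the gap. So the blank cell agrees with the text and is not a fault of the table layout.

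**2. Day of the first scheduled grade, counted from the implant.** Inputs:
- Implant to external beam, Section 4.2: "Patients enrolled in this study will undergo LDR prostate brachytherapy followed approximately 4 weeks later with hypofractionated, image-guided intensity modulated radiation therapy". Taken as 28 days.
- External beam, Section 4.3: five fractions on alternate days, weekdays only. From first to last fraction this takes 9, 10, 9, 11 or 10 days for a Monday to Friday start, so 9–11 days.
- Month 1 taken as 30 days and month 3 as 91 days after the last fraction, each ± 28 days.

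Results:
- End of external beam: 28 + 9 to 28 + 11 = day 37–39.
- Month 1: 37 + 30 to 39 + 30 = day 67–69; window 67 − 28 = 39 to 69 + 28 = 97.
- Month 3: 37 + 91 to 39 + 91 = day 128–130; window 100 to 158.

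**3. Share of the early period that passes before month 1.** This depends on where the 90 days start.
- From the implant: 67/90 to 69/90 = 74–77%. Month 1 is normally the only assessment inside the period, and a late month-1 visit (up to day 97) can miss it.
- From the implant to 90 days after external beam: 67/127 to 69/129, about 53%. Month 1 is inside; month 3 is at the edge.
- From the end of external beam: month 1 is at day 30 (2 to 58) and inside. Month 3 is at day 91 (63 to 119) and can fall on either side of day 90.

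**4. What else observes the interval.** Section 11.1 makes any urinary or rectal toxicity of grade 3 or higher an SAE. Section 17.3 requires SAE reporting from the start of study treatment until 30 days after the last treatment, which matches the nominal month-1 date. Three qualifications apply:
- The list in Section 17.3 does not repeat the grade 3 urinary or rectal criterion.
- The start of reporting is not explicitly tied to the implant. Section 5.1 calls the implant current standard procedure, although Sections 1.0 and 4.3 place it under the intervention.
- If month 1 is late (up to 30 + 28 = 58 days after external beam), only unexpected and possibly related events are reportable after day 30.

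This route does not systematically capture grade 1 or 2 events.

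**5. Primary rule.** Section 14.0 declares the treatment unsafe if 12 or more of 40 patients have the event. The exact binomial upper tail at true rates 0.15 to 0.45 gives 0.012, 0.0875, 0.2849, 0.5594, 0.7947, 0.9291 and 0.9821. The plan states 1%, 8%, 28%, 56%, 79%, 92.9% and 98.2%; all agree within one percentage point. The rule uses only the grade at 1 year, so the gap does not enter it.

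**The case against.** The strongest reply is that the interval is not unwatched and that no listed objective depends on it. Much of this stands.

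- **Severe events.** A reader might infer that acute toxicity is largely unobserved, including everything due to the implant alone. The documents do not support that. Grade 3 or higher urinary or rectal events are SAEs, a voiding trial follows the implant, there is at least one status check, and months 1 and 3 sample part of the early period.
- **First-six safety look.** A reader might infer that it rests only on the month-1 and month-3 visits. It does not: the rule in Section 11.1 counts grade 3 toxicity, which the SAE route is meant to capture.
- **Recall at month 1.** It would go too far to say that events in the gap are never graded. The plan does not say whether month-1 CTCAE records status on the day or everything since the last assessment, and patients are asked about symptoms. If it covers the whole interval, the loss is smaller. The content of the status check is likewise undefined rather than excluded.
- **Comparison with the cited series.** A reader might infer that acute rates will be biased low against the 2.3% acute grade 3 or higher GU rate in Section 3.0. That depends on how that series collected toxicity, which the documents do not show, so the inference should not be drawn.
- **Objectives.** Section 2.1 lists no acute-toxicity objective, Section 14.0 plans no acute comparison, and the Section 4.2 sentence is a radiobiological rationale.
- **Separating the components.** In a single-arm study, a grade before external beam describes the state at that point; it cannot isolate what external beam adds.
- **Repeat CTCAE before the implant.** The primary endpoint is an absolute grade, so a repeat would not alter the decision. It would only support attribution.

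What the reply does not answer is Section 12.1, which undertakes to evaluate acute toxicity and all events of grade 2 or higher. For grade 2 events in this interval, the schedule provides no contemporaneous grade.

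**Conclusion.** The point holds in a limited form. No CTCAE or IPSS assessment is scheduled between the implant and month 1, nominally 67–69 days with a window of about day 39–97. The consequence is that transient grade 1–2 toxicity is not systematically graded and that no grade is scheduled between the two radiation components. The 12-month endpoint and the 12-of-40 rule stand as they are. This is an inexpensive improvement to what the trial can report on acute toxicity, not a defect in its main decision.

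The day counts assume 28 days for the approximate four-week interval, 30 days for month 1 and 91 days for month 3. The size of the loss depends on the unstated month-1 recall interval, and the share of the early period affected (about 53% or 74–77% when counted from the implant) depends on the unstated end point or start of the 90 days.

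**What to change.** - In the Section 10.1 table, mark CTCAE v4.0 (urinary and rectal) and IPSS at the existing simulation visit, about two weeks after the implant, and at the existing status check.
- Have the month-1 visit record the worst grade since the implant as well as the current grade.
- In Section 11.1, state whether the 90-day early period starts at the implant or at the end of external beam.
- In Section 14.0, tabulate toxicity recorded before external beam separately from later toxicity, as description only.
- As a minor addition, include CTCAE in footnote 3 and Section 8.1. Hormone therapy may last up to 6 months, so the enrolment grade can be about that old at the implant.

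With these marks, scheduled grades would fall at about day 14, once between day 28 and day 37–39, and at day 67–69. The longest nominal interval would drop from 67–69 days to 30–41 days (67 − 37 = 30 if the check is at the last fraction; 69 − 28 = 41 if it is at the first).

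The cost is a change to the table and the case report form, and a few minutes of extra data entry per patient at contacts that already take place. Reported acute rates may be slightly higher.

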11.1 TOXICITIES/SIDE EFFECTS

The toxicities associated with radiation therapy to the prostate can be classified as either early (occurring within 90 days of treatment) or late (after 90 days). For the purpose of this study, the CTCAE v4.0 will be used as the primary endpoint to assess treatment-related toxicity. We expect that based on our prior studies^{14, 15}, 20% of patients of patients with have grade 2 or higher GU toxicity. The treatment will be considered to have significantly higher toxicity if ≥40% of patients in this study have ≥grade 2 at 12 months.

DEFINITIONS:

1. Adverse Event (AE)
 - a. An AE is defined by the GCP (Guide to Good Clinical Practice) as any undesirable experience occurring to a subject during a clinical trial, whether or not it is considered related to the investigational product(s).
2. Serious Adverse Event (SAE)
 - a. An SAE is an adverse experience that:
 - i. Is fatal or life-threatening
 - ii. Is disabling
 - iii. Results in hospitalization or prolongation of hospitalization
 - iv. Results in a congenital anomaly or occurrence of malignancy
 - v. Any urinary or rectal toxicity that is grade 3 or higher
3. Unexpected Adverse Event (UAE)
 - a. A UAE is an experience not previously reported (in nature, severity, or incidence) in the current Investigator's Brochure or general investigational plan.

Toxicities associated with radiation treatment include increased urinary frequency, urgency, weak stream, and nocturia. Other toxicities that may be related to radiation are fatigue, dysuria, hematuria, erectile dysfunction, urinary obstruction (due to edema or stricture), proctitis, bowel

injury or secondary cancers. Urinary, rectal, and erectile toxicities will be measured using IPSS, CTCAE v 4.0, and EPIC validated instruments (appendix).

The probability of severe (grade 3 or higher) urinary or rectal toxicity is expected to be $\leq 5\%$ which is currently observed rate of severe toxicity reported using standard combined brachytherapy and conventionally fractionated external beam radiation at MSKCC.¹⁴

To insure that unexpected significant toxicity is identified as early as possible with this treatment, we will observe the first 6 patients for a minimum of 3 months before enrolling any additional patients. If more than one patient has a grade 3 toxicity, we will wait 12 months before resuming accrual. If 4 or more patients of the first 6 patients have grade 3 or higher toxicity at 3 months we will terminate the study.

Evaluation of SAE:

Review of the patient record including treatment dosimetry (brachytherapy and external beam radiation) will be undertaken by the principal investigator and investigators of the study. The PI in conjunction with the investigators may decide to continue the protocol without modification, discontinue the study altogether, or modify the protocol prior to enrolling more patients pending the results of the review based on the criteria state in section 14.0.

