14.0 BIOSTATISTICS

The primary objective is to assess the toxicity of hypofractionated radiation therapy in combination with brachytherapy for the treatment of intermediate risk prostate cancer. To set up a decision rule we will focus on the CTCAE v 4.0 (see appendix) grade 2 or higher GU toxicity observed at the 1-year follow-up time (+/- 4 weeks). We will enroll 40 evaluable patients, and if 12 or more patients have a CTCAE v4.0 grade 2 or higher toxicity at 1 year, this treatment will be deemed too toxic and the study will be stopped. Otherwise it will be declared safe. This decision rule has the following probabilities of declaring treatment unsafe

True toxicity rate	0.15	0.20	0.25	0.30	0.35	0.40	0.45
Probability of declaring unsafe	1%	8%	28%	56%	79%	92.9%	98.2%

Patients who withdraw, die due to reasons other than toxicity, or fail to provide the 1-year CTCAE v4.0 GU toxicity status will be replaced by new patients. To this end we may need to enroll an additional 4 patients (10%).

For the secondary objectives, all toxicities will be tabulated by type and grade. Post-treatment PSA values will be summarized numerically and graphically. Time to PSA relapse will be analyzed by Kaplan-Meier estimation. The pathologic response rates at 24-36 months will be calculated as sample proportion based on the available patients and confidence intervals will be provided. Erectile function evaluated by IIEF will be summarized by descriptive statistics.

It is expected that it will take approximately 3 years to accrue the total of 45 patients.

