17.3 Serious Adverse Event (SAE) Reporting

An adverse event is considered serious if it results in ANY of the following outcomes:

- Death
- A life-threatening adverse event
- An adverse event that results in inpatient hospitalization or prolongation of existing hospitalization
- A persistent or significant incapacity or substantial disruption of the ability to conduct normal life functions
- A congenital anomaly/birth defect
- Important Medical Events (IME) that may not result in death, be life threatening, or require hospitalization may be considered serious when, based upon medical judgment, they may jeopardize the patient or participant and may require medical or surgical intervention to prevent one of the outcomes listed in this definition

Note: Hospital admission for a planned procedure/disease treatment is not considered an SAE.

SAE reporting is required as soon as the participant starts investigational treatment/intervention. SAE reporting is required for 30-days after the participant's last investigational treatment/intervention. Any event that occurs after the 30-day period that is unexpected and at least possibly related to protocol treatment must be reported.

Please note: Any SAE that occurs prior to the start of investigational treatment/intervention and is related to a screening test or procedure (i.e., a screening biopsy) must be reported.

All SAEs must be submitted in PIMS. If an SAE requires submission to the HRPP office per IRB SOP RR-408 „Reporting of Serious Adverse Events”, the SAE report must be submitted within 5 calendar days of the event. All other SAEs must be submitted within 30 calendar days of the event.

The report should contain the following information:

- The date the adverse event occurred
- The adverse event
- The grade of the event
- Relationship of the adverse event to the treatment(s)
- If the AE was expected
- Detailed text that includes the following
 - An explanation of how the AE was handled
 - A description of the participant's condition
 - Indication if the participant remains on the study
- If an amendment will need to be made to the protocol and/or consent form
- If the SAE is an Unanticipated Problem

For IND/IDE protocols: The SAE report should be completed as per above instructions. If appropriate, the report will be forwarded to the FDA by the IND Office

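### After the first six patients, SAE decisions are referred to section 14.0, which has no rectal criterion and none for grade 3+ urinary toxicity separate from grade 2

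*Combined protocol and SAP*

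**What the plan says.** Section 11.1 sets the expectation: "The probability of severe (grade 3 or higher) urinary or rectal toxicity is expected to be" 5% or less. The same section lists among its SAE criteria "Any urinary or rectal toxicity that is grade 3 or higher".

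Its counts specific to grade 3+ sit in one paragraph about observing the first six patients for at least 3 months. First, "If more than one patient has a grade 3 toxicity, we will wait 12 months before resuming accrual". Then, "If 4 or more patients of the first 6 patients have grade 3 or higher toxicity at 3 months we will terminate the study". The hold sentence names neither a cohort nor a time point.

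Under Evaluation of SAE, the investigators review each case, including dosimetry, and may carry on, change or end the study before more patients enter, "pending the results of the review based on the criteria state in section 14.0".

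Section 14.0 contains one decision rule: "if 12 or more patients have a CTCAE v4.0 grade 2 or higher toxicity at 1 year, this treatment will be deemed too toxic". The sentence before it and the replacement rule after it show that the endpoint is GU toxicity. All other toxicities are only tabulated by type and grade.

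Two further safeguards are described. Section 16.3 places Phase I and II trials under the DSMC, with monitoring procedures fixed at activation and not reproduced. Section 17.3 adds: "Any event that occurs after the 30-day period that is unexpected and at least possibly related to protocol treatment must be reported". Section 11.1 defines unexpected to include incidence, but gives no figure for excess incidence.

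**The concern.** The protocol says that decisions after a severe urinary or rectal event rest on criteria in section 14.0. For a rectal event, that section has none. For a severe GU event, it has only a rule that weighs grade 3+ the same as grade 2 and reads status at 1 year. Once the run-in is over, the document therefore states no count at which severe toxicity above the expected 5% is recognised and acted on, while up to 45 - 6 = 39 more patients may be treated.

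The run-in does not fill the gap. Its minimum observation is 3 months, and section 11.1 defines late toxicity as starting after 90 days, so it can clear before the late toxicity named in the primary objective appears. Case review and the unexpected-incidence test would both be applied more consistently against a stated number.

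**Working it through.** **1. The plan's own figures.** For X ~ Binomial(40, p), P(X ≥ 12) is 1.2%, 8.75%, 28.5%, 55.9%, 79.5%, 92.9% and 98.2% at p = 0.15 to 0.45 in steps of 0.05. Section 14.0 prints 1%, 8%, 28%, 56%, 79%, 92.9% and 98.2%. The table reproduces.

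**2. What the 12-of-40 rule sees of severe toxicity.** Two scenarios bracket it:
- Total GU grade 2+ stays at the expected 20%: declared safe in 1 - 0.0875 = 91%, whatever share is grade 3+. As many as 11 of 40 (27.5%) could have grade 3+ GU toxicity at 1 year without reaching the limit.
- Grade 2 stays at 21% (the late GU figure in section 3.0, assumed to apply at 1 year) and grade 3+ GU rises to 10%, 15% or 20%: pooled rates are 31%, 36% and 41%, and P(X ≥ 12) = 61%, 83% and 94%.

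In both, the rule needs 1-year status, so it acts late. No number of rectal events reaches it.

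**3. First-six rules.** With n = 6 and every severe event falling inside the run-in:

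| True severe rate | Hold or terminate, P(X ≥ 2) | Terminate, P(X ≥ 4) |
|---|---|---|
| 5% | 3.3% | 0.01% |
| 10% | 11.4% | 0.13% |
| 15% | 22.4% | 0.6% |
| 20% | 34.5% | 1.7% |

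These are upper limits. Now assume onset uniform over 12 months and entry at 45/36 = 1.25 patients per month, so entries are 0.8 months apart. When the sixth patient reaches 3 months, the six have been observed for 3.0, 3.8, 4.6, 5.4, 6.2 and 7.0 months, and each has event probability p × months/12. The chance of two or more is then about 2% at p = 10% and 8% at p = 20%.

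**4. Scope of the hold sentence.** It speaks of resuming accrual and stands between two sentences on the first six, so it is read as part of the run-in. Applied to all 45, P(X ≥ 2) would be 66.5% at 5%, making a 12-month halt likely at the expected rate.

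**5. A cumulative trigger.** At each number implanted n, take the smallest k with P(X ≥ k | n, 5%) ≤ 3%. This gives 3 for n = 6-13, 4 for 14-24, 5 for 25-35 and 6 for 36-45. The largest tail is 2.98%, at n = 24.

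The exact column below assumes all outcomes are known at once, with no look before n = 6. The other columns simulate crossing before accrual ends (100,000 runs, 1.25 patients per month, no withdrawals after implant). In each pair, the first figure has no implant lag and a 3-month pause after patient 6. The second has a 2-month lag and a 6.5-month gap (2 to implant + 1.5 to the end of external beam + 3, since section 10.1 times follow-up from the last external-beam day).

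| True rate | Exact | 12-month onset | 24-month onset |
|---|---|---|---|
| 5% | 6.0% | 2.3% / 2.0% | 0.6% / 0.6% |
| 10% | 38.8% | 21.9% / 19.1% | 9.1% / 7.3% |
| 15% | 75.2% | 55.1% / 49.9% | 31.8% / 26.5% |
| 20% | 93.3% | 81.3% / 77.1% | 58.5% / 51.9% |

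Mean enrolment without lag at 10%, 15% and 20% is about 41, 35 and 28 with 12-month onset, and 44, 41 and 37 with 24-month onset.

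**The case against.** The strongest reply is that review already starts at the first severe event. Each grade 3+ urinary or rectal event is an SAE, its review includes dosimetry, and the investigators can stop or change the study before anyone else enters. The DSMC also oversees the trial, and its activation-time procedures are not shown, so a number may exist there. This stands. A reader might infer that severe toxicity after patient 6 would go unwatched; the documents do not support that. What is missing is a stated count, and a cross-reference that fits the events sent through it.

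A second tempting inference is that the 12-of-40 rule is blind to severe GU toxicity. It is not: it counts those events, and if grade 2 holds at 21% it fires in 61% to 94% of trials as grade 3+ GU goes from 10% to 20%. The 91% declared-safe figure needs total grade 2+ to stay at 20%. Neither scenario helps with rectal events or brings action forward.

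Third, the hold sentence read literally could apply beyond the first six. The 66.5% shows that this reading would be burdensome, not that it was unintended. Context favours the run-in, and the finding depends on that reading.

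Fourth, the 3% pointwise limit is a choice not drawn from the documents, and the trigger is weak against a doubling: it misses 78-93% of trials at a true 10% during accrual. Both are fair. A smaller repair would correct the reference and compare cumulative incidence with 5%, but would still leave open when an excess is declared.

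**Conclusion.** The point holds as a gap in a stated safety rule and should be corrected. SAE decisions are said to rest on section 14.0, which has no rectal criterion and no grade 3+ GU criterion apart from grade 2. After the run-in, no count in the document triggers action on severe urinary or rectal toxicity above 5%.

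The size depends on assumptions. The run-in hold catches at most 11.4% of trials at a true 10% and 34.5% at 20%, and about 2% and 8% if onset is spread over 12 months. Cover from the 12-of-40 rule ranges from little to considerable for GU events, always late, and is nil for rectal ones. Severe rates above 5% are illustrative: section 3.0 reports 2.3% acute and 3.1% late grade 3+ GU toxicity with the conventional combination, and nothing in the documents suggests that the true rate here is higher. Accrual pace, implant lag and onset patterns are likewise assumed. Confidence is medium, because the hold sentence must be read as part of the run-in and the DSMC procedures cannot be seen.

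**What to change.** Add to section 14.0, with cross-references from section 11.1 and Evaluation of SAE, a cumulative trigger. Count patients with a treatment-related grade 3+ urinary or rectal event at any time after implant. Pause accrual for DSMC review at:
- 3 patients with 6-13 implanted
- 4 with 14-24
- 5 with 25-35
- 6 with 36-45

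Index to patients implanted, not enrolled, because section 4.3 allows up to 6 months of hormone therapy before implant. With 14 enrolled but 10 implanted, an enrolment index would demand 4 patients instead of 3; at a true 20%, P(X ≥ 3 | n = 10) = 32.2% against P(X ≥ 4 | n = 10) = 12.1%.

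State that the more-than-one-patient hold refers to the first six and takes precedence during the run-in, where the new trigger alone would need 3. Leave the first-six and 12-of-40 thresholds unchanged. Print the operating characteristics with their assumptions, including the 10% row and mean enrolment, and say plainly that sensitivity to a doubling or to late onset is limited.

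The cost is protocol wording. CTCAE grading at follow-up visits (section 10.1), attribution of grade 2+ events (section 12.1) and the DSMC (section 16.3) are already in the plan. The downside is an unnecessary pause in about 1-6% of trials at a true 5%: 0.6% during accrual with 24-month onset, 2.3% with 12-month onset, and 6.0% if all outcomes were known at once.
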